## **3.2 Exclusion Criteria**

The presence of any of the following conditions will exclude a subject from study enrollment:

- 3.2.1 Concurrent, acute, active opportunistic infection other than oral thrush or genital herpes within 14 days of enrollment.
- 3.2.2 Symptomatic visceral KS requiring cytotoxic therapy.
- 3.2.3 Concurrent neoplasia requiring cytotoxic therapy.
- 3.2.4 Acute treatment for an infection (other than oral thrush or genital herpes) or other serious medical illness within 14 days prior to enrollment.
- 3.2.5 Anti-neoplastic treatment for KS (including chemotherapy, radiation therapy, local therapy, biological therapy, or investigational therapy) within 4 weeks of study entry.
- 3.2.6 Previous local therapy of any KS-indicator lesion within 60 days prior to enrollment unless the lesion has clearly progressed since treatment. Any prior local treatment to indicator lesions regardless of the elapsed time should not be allowed unless there is evidence of clear-cut progression of said lesion.

- 3.2.7 Use of any investigational drug or treatment (excluding antiretroviral therapy or agents available on a treatment IND) within 28 days prior to enrollment.
- 3.2.8 A history of any of the following: myocardial infarction, severe/unstable angina, coronary/peripheral artery bypass graft, symptomatic congestive heart failure, cerebral vascular accident, or transient ischemic attack, pulmonary embolism, deep vein thrombosis, or other significant thromboembolic event.
- 3.2.9 Known coagulopathy or bleeding diathesis.
- 3.2.10 Known history of drug-induced liver injury.
- 3.2.11 Any history of the following: central nervous system, pulmonary, gastrointestinal, or urinary bleeding.
- 3.2.12 Resting systolic blood pressure >160 mmHg or diastolic blood pressure >100 mmHg.
- 3.2.13 Female patients who are pregnant or breast-feeding.
- 3.2.14 Prior or ongoing clinically significant illness, medical condition, surgical history, physical finding, ECG finding, or laboratory abnormality that, in the investigator's opinion, could affect the safety of the subject; alter the absorption of the study drug; or impair the assessment of study results.
- 3.2.15 Major surgery within 30 days prior to enrollment, the presence of unhealed surgical wounds at the time of enrollment or anticipated need for surgical procedures during the period of study participation.
- 3.2.16 Ongoing systemic corticosteroid treatment, other than replacement doses.
- 3.2.17 Ongoing use of anticoagulant therapy, including coumadin, heparin or antiplatelet drugs. Note: Use of aspirin or nonsteroidal anti-inflammatory drugs (NSAIDs) at doses not to exceed the maximum recommended dose is permitted.

### **3.3 Number of Subjects to be Enrolled**

- 3.3.1 Three to 38 evaluable subjects will be enrolled. In Stage 1, three successive cohorts of three subjects have been enrolled at each of the following dose levels: 40 mg/dose BID, 80 mg/dose BID, and 100 mg/dose BID. An additional eight subjects have been enrolled in Stage 2 at the highest safely tolerated dose (e.g., 100 mg/dose BID) established in Stage 1 to better define the safety, antitumor activity, and biological activities of PTC299 at this dose level. Dose escalation will continue in Stage 3 for two additional successive cohorts of 3 to 6 subjects at the following dose levels: 160 mg/dose TID and 200 mg/dose TID. Once the safety profile at each level has been established based on first cycle dose-limiting toxicities (DLTs), an additional 9 to 12 subjects will be enrolled at the highest safely tolerated dose (e.g., 200 mg/dose TID) for a total number of 15 subjects at this dose level. If the dose level of 200 mg/dose TID is not well tolerated (i.e.,  $\geq 2/6$  subjects experience a first-cycle DLT), an additional 9 to 12 subjects will be enrolled at the dose level of 160 mg/dose TID for a

total number of 15 subjects at the MTD. If the dose level of 160 mg/dose TID is not well tolerated in the initial cohort (e.g.,  $\geq 2/3$  or  $\geq 2/6$  subjects experience a first-cycle DLT), 3 to 15 subjects will be enrolled at the dose level of 120 mg/dose TID. If the dose level of 120 mg/dose TID is not well tolerated (e.g.,  $\geq 2/3$  or  $\geq 2/6$  subjects experience a first-cycle DLT), a total of 9 to 15 subjects will be enrolled at the 100 mg/dose BID dose level in Stage 3. Collectively, up to 21 patients will be enrolled in Stage 3.

- 3.3.2 Estimated accrual rate: four subjects per month.
- 3.3.3 Replacement of subjects who cannot be evaluated: A subject who does not complete cycle 1 can be replaced if, based on a review of the available safety for that dose level, the principal investigator agrees that the events leading to subject withdrawal are unlikely to constitute a safety risk for further subject enrollment and dose escalation. This means that as long as subject safety is not compromised, a subject who withdraws from the study for administrative reasons prior to experiencing DLT during cycle 1 of therapy can be replaced by another subject to complete the number of subjects evaluable per dose level required by the protocol. Similarly, as long as subject safety is not compromised, if an eligibility criterion or protocol violation occurs that substantially impairs evaluation of DLT during cycle 1, another subject can enter the cohort to complete the number of subjects evaluable per dose level required by the protocol. Any replacement subject will be enrolled into the same dosing cohort as that for the subject who withdrew. Patients withdrawn because of PTC299-related DLT may not be replaced.

### **3.4 Subject Enrollment Procedures**

This trial is open to all AMC sites for subject accrual. Sites must have this protocol approved by their Institutional Review Boards (IRB) and be registered with the AMC Operations Center before they may enroll subjects.

After the subject has signed the informed consent and it has been determined that the subject is eligible, the subject must be registered on-line via the AMC AdvantageEDCSM Internet Data Entry System. Enrollment and data collection will occur via the AMC Internet Data Entry System.

The participating site will ensure the subject meets all eligibility criteria prior to completing the protocol-specific eligibility checklist. Subjects will be enrolled on-line via the AMC Internet Data Entry System no more than 1 week prior to the initiation of treatment (enrollment 1 day prior to or on the day of treatment is strongly encouraged). Once the eligibility checklist is submitted a system generated confirmation email will be sent to the enroller upon successful completion of the subject enrollment. If the on-line system is inaccessible, the site should notify the AMC Operations Center (via email at [[contact]](mailto:[contact]) or via phone at [contact]) for further instructions.

## 4.0 CLINICAL AND LABORATORY EVALUATIONS

All signs, symptoms, HIV-related and AIDS-defining events (refer to Appendix XII), death and toxicities must be documented. All signs, symptoms and laboratory results  $\geq$  Grade 2 that are felt to be clinically significant or drug-related and all HIV-related and AIDS-defining events and deaths must be recorded on the case report forms (CRFs).

All prescription medications taken within 14 days prior to study enrollment and during the interval between each visit must be recorded on CRFs. The duration of all anti-HIV medications and all opportunistic infection (OI) treatment and/or prophylaxis medications at the time of enrollment must be recorded in the CRF. All non-prescription medications must be recorded in the clinic record.

### 4.1 Screening/Baseline Evaluations

4.1.1 Biopsy diagnostic of KS at any time prior to study entry.

4.1.2 Documentation of HIV infection at any time prior to study entry.

4.1.3 Chest X-ray to rule out pulmonary KS (must be done within 28 days prior to study enrollment). Pulmonary involvement must be asymptomatic or minimally symptomatic and not require systemic cytotoxic therapy in the judgment of the Investigator. Subjects with a positive chest X-ray or symptoms suggestive of pulmonary disease will have a chest CT performed at entry. Findings suggestive of pulmonary KS should be followed up with bronchoscopy to evaluate the presence and extent of pulmonary KS and evaluate for the presence of other pulmonary diseases.

4.1.4 Electrocardiogram within 21 days of enrollment.

4.1.5 A medical history within 21 days of starting study drug to include the following information:

- Previous HIV-related and non-HIV related diagnoses.
- Complete prior anti-HIV therapy, immune based therapy and prior anti-tumor therapy, including start dates of current anti-HIV therapy.
- All prescription medications taken within the preceding 2 weeks.
- An assessment of signs and symptoms occurring within the 2 weeks prior to beginning study drug, including history of weight change.
- Complete physical exam including the following: vital signs (temperature, pulse, blood pressure, respiratory rate), height, weight, and Karnofsky performance status (Appendix II).

4.1.6 Laboratory studies must be obtained within 21 days (unless noted otherwise) prior to beginning study drug and will include the following:

- Complete blood count with differential and platelets.
- INR and aPTT.
- Serum chemistries: liver enzymes (AST, ALT, alkaline phosphatase), BUN, creatinine, electrolytes (sodium, potassium, chloride, bicarbonate), calcium,

phosphorus, total protein, glucose, albumin, bilirubin (direct and indirect), triglycerides and total cholesterol.

- Blood for ACTH and cortisol.
- Urinalysis.
- For women of child bearing potential, a serum beta human chorionic gonadotropin ( $\beta$ -HCG) pregnancy test within 72 hours of initiating treatment.
- CD4 count.
- Plasma HIV-1 RNA.

4.1.7 KS tumor assessments may be performed on Day 1 prior to receiving study medication but may be performed no earlier than 14 days before initiating treatment. Tumor measurements should include the following:

- Identify marker lesions: Select five bi-dimensionally measurable marker lesions for assessing changes in lesion dimension. Select the largest lesions with clearly defined margins. Marker lesions will be photographed to document lesion appearance and affected areas at baseline, in accordance with the guidelines for photography in Appendix XIV. Additionally, patients will need a sufficient number of non-indicator cutaneous lesions measuring  $\geq 4 \times 4$  mm to obtain a total of four (4) 3-mm punch biopsies, two at baseline and two during the course of treatment.
- For subjects with  $< 50$  total skin and oral lesions, all lesions must be evaluated for changes in number and characteristics. For subjects with  $\geq 50$  total skin and oral lesions, choose up to three representative areas for evaluating change in lesion numbers and characteristics (preferably an area with  $\geq 5$  lesions), with a total of at least 20 lesions.

NOTE: A representative area is a single extremity, the back, chest, or face that has lesions similar in characteristics, i.e., nodularity, size, color, and number, to those found on other parts of the body. A representative area does not need to be the area with the largest number of lesions but should contain lesions that are truly representative of those throughout the remainder of the body.

4.1.8 Staging Criteria (to be done within 28 days prior to study enrollment). KS staging will be based on the modified AIDS Clinical Trials Group (ACTG) Oncology Committee Staging Criteria (see Appendix III).

4.1.9 If specific consent obtained (see Appendix VIII), specimens for the AIDS and Cancer Specimen Resource (ACSR) will be collected within 28 days prior to enrollment (see Appendix VII for specimen handling).

4.1.10 KSHV viral load (see Appendix VI).

## 4.2 Evaluations During Treatment

Evaluations may occur up to 3 days before or after the end of the study visit indicated, unless otherwise noted. Each cycle will be 28 days. Evaluations will continue as outlined below.

- 4.2.1 Clinical assessment at Days 15 ( $\pm$  2) of cycle 1, and then Day 1 on cycle 2 and every cycle thereafter to include an assessment of the following at every visit unless otherwise specified:
- 4.2.1.1 KS tumor assessment Day 1 of cycle 2 and every cycle thereafter. Response of KS to treatment will be assessed as described in Section 8.0. Photographic documentation of lesions will be completed at each visit when the KS response category changes. For example, if a participant's KS response category changes from no response (stable disease) to partial response, the site will take photos of this to document the category change. If there was no change in the KS response category, no photos are required. Refer to Appendix XIV for lesion photography guidelines.
  - 4.2.1.2 A complete physical exam including: vital signs, weight, Karnofsky performance status (Appendix II) and toxicity evaluation.
  - 4.2.1.3 Signs and symptoms review.
  - 4.2.1.4 Complete blood count with differential and platelets.
  - 4.2.1.5 INR and aPTT.
  - 4.2.1.6 Serum chemistries: liver enzymes (AST, ALT, alkaline phosphatase), BUN, creatinine, electrolytes (sodium, potassium, chloride, bicarbonate), calcium, phosphorus, glucose, total protein, albumin, bilirubin (direct and indirect), triglycerides and total cholesterol. If the triglycerides and/or total cholesterol increases to  $\geq$  grade 3, then these values should be rechecked in a fasting state and the cholesterol fractionated.
  - 4.2.1.7 Urinalysis
  - 4.2.1.8 For women of childbearing potential: serum  $\beta$ -HCG at any time pregnancy is suspected.
  - 4.2.1.9 All HIV-related and AIDS-defining events (Appendix XII) and concomitant prescription and over the counter medications, vitamins and supplements taken since the last visit.
  - 4.2.1.10 CD4 count on Day 29 (Day 1 of cycle 2) and every three cycles (12 weeks) thereafter.
  - 4.2.1.11 Plasma HIV-1 RNA on Day 29 (Day 1 of cycle 2) and every three cycles (12 weeks) thereafter.
  - 4.2.1.12 KSHV viral load on Day 29 (Day 1 of cycle 2) and every three cycles (12 weeks) thereafter.

4.2.1.13 Blood for ACTH and cortisol on Day 29 (Day 1 of cycle 2) and every cycle thereafter.

#### 4.2.2 Biologic Endpoints

4.2.2.1 A 3-mm punch biopsy of a non-indicator KS lesion will be performed at baseline and between Days 22 and 28 of cycle 1. Biopsies will be fixed in formalin and studied by immunohistochemistry (IHC) for expression of the following: VEGF, VEGFR-2, VEGFR-3, phospho-Akt, KSHV LANA, orf59, p53 and HIF-1 $\alpha$ . Tumor cell proliferation will be assessed by Ki-67 staining. Change in the intensity or distribution of a particular marker will be evaluated. Ki 67 staining will be quantified as a percentage of tumor cells. All other immunohistochemical staining will be described with a score (0, 1+, 2+) and a description of the distribution of the signal (endothelial cells, spindle cells, infiltrating lymphocytes, etc.). Depending on the results of these assays, other potential immunohistochemical markers characteristic for KS may also be measured. A detailed protocol is provided in Appendix XIII.

Evaluation by IHC of the effects of PTC299 on KSHV LANA and orf 59 is based on the hypothesis that either VEGF depletion directly, or VEGF inhibition-induced hypoxia indirectly, may induce KSHV lytic gene expression. Because reduction of VEGF production is expected to reduce capillary-dependent oxygen flow to the tumor, this will, in turn, induce hypoxia. Hypoxia causes p53-dependent apoptosis but also, via HIF-1 $\alpha$ , induces VEGF. HIF-1 $\alpha$  and the cellular response to hypoxia are modulated by KSHV. Hence, p53, HIF-1 $\alpha$ , and some of their representative targets will be characterized by IHC as secondary biological endpoints.

4.2.2.2 A separate 3-mm biopsy of a non-indicator KS lesion will be performed at baseline and again between Days 22 and 28 of cycle 1 to assess viral gene expression within tumor at the messenger RNA level. Real-time QPCR based profiling of KSHV transcription will be used to test the hypothesis that depletion of VEGF directly or indirectly through the induction of hypoxia may lead to changes in KSHV transcription. This has previously been observed in laboratory studies.[134-137] A detailed protocol is provided in Appendix V.

4.2.2.3 Using the same biopsies as described in Section 4.2.2.2, Real-time QPCR based profiling will be used to test the hypothesis that depletion of VEGF directly, or indirectly through the induction of hypoxia, may lead to changes in cellular gene transcription.

4.2.2.4 In addition, as a control, a 3-mm skin biopsy from morphologically normal skin in the same anatomic location as the tumor specimen will be obtained at baseline only. A detailed protocol is provided in Appendix V.

#### 4.2.3 Pharmacokinetics of PTC299

Blood for PK assessments should be collected immediately pre-dose; and at 1, 2, 3, 4, 5, 6, and 8 hours after the AM dose on Day 1 and again at 1, 2, 3, 4, 5, 6, and 8 hours after the AM dose on Day 28 of cycle 1. (**Note:** the Day 28/cycle 1 PK samples can be collected up to 3 days prior to Day 28). A PK sample will also be collected prior to the AM dose on Day 15 ( $\pm$  1 day) during cycle 1 and prior to the AM dose on Day 28 of cycle 2 (or Day 1 of cycle 3 if the subject's last dose of study treatment was the evening prior). Blood samples for PTC299 PK assessments will not be collected after cycle 2. The actual sample collection times should be recorded. Please see Appendix IX for detailed collection, processing, storage and shipping instructions for PK samples.

4.2.4 Assaying secreted cytokines characteristic for KS: To measure PTC299's effect on KS we will evaluate serum and plasma for levels of the cytokines (e.g., VEGF-A, VEGF-C, VEGF-D, VEGF-R1, VEGF-R2, VEGF165b, PlGF, IL-6, and IL-8) at baseline (pre-dose of study treatment on Day 1) and mid-cycle (Day 15) of cycle 1, on Day 1 of all subsequent cycles, and at the time of treatment discontinuation and 30 days post discontinuation of study therapy. Please see Appendix IV for detailed collection, processing, storage and shipping instructions for these samples. Depending on the results of these assays, other potential serum markers characteristic for KS may also be measured.

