The specific mechanism of action accounting for the PTC299 effect on VEGF remains an area of ongoing investigation. Available data suggest that the presence of the 5'-UTR in the VEGF mRNA is required to observe the PTC299 inhibitory actions on luciferase or VEGF protein production. Activity is clearly post-transcriptional; real-time quantitative polymerase chain reaction (QPCR) assessments of mRNA have shown that PTC299 does not alter the levels of VEGF message. Analyses of its effects on ribosome association with VEGF transcripts indicate that PTC299 does not impede initiation of VEGF translation or promote disassociation of ribosomes from VEGF mRNA.

PTC299 also provokes a late G1/early S-phase cell cycle delay (i.e., between the late resting or pre-DNA synthesis phase, and the early DNA synthesis phase) in those tumor cell lines in which VEGF generation is decreased by the drug. Further characterization indicates that this effect is concentration dependent, occurring at low-nanomolar EC50 values similar to those associated with reducing VEGF production. The effect is seen by 14 to 18 hours after PTC299 treatment, with reversion to normal cell cycle progression by ~24 hours after cessation of drug exposure. The cell cycle delay and inhibition of VEGF protein production occur in concert, linking these phenotypes in tumors. Interestingly, inhibition of VEGF production in these same tumor cells with small interfering RNA (siRNA) does not induce a cell cycle delay. Conversely, mimosine, a DNA synthesis inhibitor that halts cell cycle progression at the G1/S interface, does not reduce VEGF production. Thus, current evidence indicates that the effects of PTC299 on the tumor cell cycle occur in parallel with its actions on VEGF production in tumors.

Additional studies are in progress to determine the molecular target of PTC299 and to determine how the drug acts to inhibit tumor VEGF production and delay tumor cell cycling.

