**Figure 2. Plasma Concentrations of PTC299 by Fed/Fasted Status after a 1.0-mg/kg Dose of PTC299 in Healthy Volunteers**

Abbreviation: SD = standard deviation

PK parameters for PTC299 in plasma are shown in Table 1. The mean  $T_{max}$  was in the range of 3 to 6 hours. During Stage 1, mean values for  $C_{max}$  and AUC rose steadily with dose. Increases in mean  $C_{max}$  values were generally dose proportional. Increases in mean  $AUC_{0-24}$  values were somewhat greater than dose proportional through the body-weight-adjusted (mean total) 1.00-mg/kg (75 mg) dose level and then less than dose proportional in the transition from the 1.00-mg/kg (75 mg) to the 3.00-mg/kg (203 mg) dose levels. The PTC299 plasma-concentration time course was well described by a 2-compartment model. Fitting of individual subject data resulted in a mean half-life during the distribution phase ( $t_{1/2\alpha}$ ) of ~3 hours and a terminal half-life ( $t_{1/2\beta}$ ) in the range of 28 to 56 hours.

As also shown in Table 1, ingestion of a high-fat, high-calorie meal just prior to administration of a body-weight-adjusted (mean total) 1mg/kg (75 mg) of PTC299 in Stage 2 increased the mean  $C_{max}$  by ~40% but did not materially change other PK parameters.

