If a subject experiences a DLT during the 28-day course of PTC299 therapy, then study drug administration can be omitted, as necessary, until the adverse event resolves or stabilizes to an acceptable degree (i.e., to < Grade 2). Thereafter, the dose of PTC299 for the remainder of the treatment course during that cycle should be reduced by one dose level; reduction to Dose Level -1 (20 mg/dose BID) may be made for subjects experiencing PTC299-related DLT at Dose Level 1 (40 mg/dose BID); and reduction to Dose Level 4 (100 mg/dose BID) may be made for subjects experiencing PTC299-related DLT at Dose Level 5 (120 mg/dose TID) and reduction to Dose Level 6 (160 mg/dose TID) may be made for subjects experiencing PTC299-related DLT at Dose Level 7 (200 mg/dose TID). Doses during missed days of treatment should not be made up (e.g., if a subject experiences an AE on Day 7 of the treatment course and the event lasts for 3 days, the reduced dose should be administered only for a further 18 days so that the total treatment course duration remains 28 days).

A new cycle of PTC299 treatment may begin when AEs or laboratory abnormalities have returned to baseline levels. If AEs or laboratory abnormalities are not resolved to baseline, week-by-week delays in initiating the new cycle of treatment should be instituted. If it takes longer than 4 weeks for the AE to resolve to baseline, protocol treatment will be permanently discontinued. Once all toxicities have returned to baseline, the next cycle of therapy can be initiated.

Subjects experiencing any of the DLTs described in Section 5.3.3 in the current cycle of therapy should have the dose in the next cycle of therapy reduced by 1 dose level; reduction to Dose Level -1 (20 mg/dose BID) may be made for subjects experiencing PTC299-related DLT at Dose Level 1; reduction to Dose Level 4 (100 mg/dose BID) may be made for subjects experiencing PTC299-related DLT at Dose Level 5 (120 mg/dose TID) and reduction to Dose Level 6 (120 mg/dose TID) may be made for subjects experiencing PTC-related DLT at Dose Level 7 (160 mg/dose TID).

In general, after a dose is reduced for PTC299-related toxicity it should not be re-escalated, even if there is minimal or no toxicity with the reduced dose. However, if further evaluation reveals that the adverse event that led to the dose reduction was not study drug-related, the dose may be re-escalated to the original dose level.

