## 11.2 Statistical Analysis Plan

Descriptive statistics will be used to summarize the demographic and baseline characteristics of the study population. Subjects who do not complete the required observations will be described and evaluated separately, as necessary. Reasons for study discontinuation and date of withdrawal from study will be described

The binomial proportion and its 95% confidence interval will be used to estimate the objective (complete + partial) response rate as defined in Section 8.0. With 12 patients at the maximally treated dose, the response rate can be estimated with a 95% confidence interval with width no greater than  $\pm 28.3\%$ .

The effects of PTC299 on serum and plasma VEGF, VEGFR and cytokine profiles will be evaluated by comparing the Day 28 value with the pre-treatment value, and the Day 28 value with the lowest value obtained subsequent to Day 28. These changes will be evaluated using the paired t-test, or if the data are not normally distributed, the Wilcoxon signed rank test. Comparisons between dose levels with respect to these changes will be evaluated using ANOVA or the Kruskal-Wallis test if the data are not normally distributed.

Comparisons of on-treatment values with the pre-treatment baseline value, and with the corresponding baseline value within each cycle will be performed using paired t-tests. If the distribution of the data deviates substantially from normality, the analysis will be performed on log-transformed data. Differences in change from baseline among dose levels will be analyzed by means of ANOVA (including a test for linear dose response); if a significant effect is observed, individual comparisons among dose levels will be performed with t-tests. The pattern of responses across doses will be considered in interpreting the logical validity of the results. Results will be presented in tabular and graphic form, as appropriate.

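### The Day 28 cytokine value in Section 11.2 has no Day 28 sample behind it; the nearest draw is tied to the start of cycle 2, which may be delayed and so fall off drug

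*Combined protocol and SAP*

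**What the plan says.** Section 11.2 evaluates circulating VEGF, VEGFR and cytokines by "comparing the Day 28 value with the pre-treatment value", and by comparing the Day 28 value with the lowest value seen afterwards.

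Section 4.2.4 sets the cytokine draws: pre-dose on Day 1, then "mid-cycle (Day 15) of cycle 1, on Day 1 of all subsequent cycles, and at the time of treatment discontinuation", and once more 30 days after stopping. In Appendix I the cycle 1 Day 28 column holds only the two KS biopsies and PK sampling. The cytokine row resumes in the next column, headed as both Day 29 and Day 1 of cycle 2.

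Those two labels can separate. Section 5.3.4 says: "If AEs or laboratory abnormalities are not resolved to baseline, week-by-week delays in initiating the new cycle of treatment should be instituted". It ends protocol treatment only when resolution takes more than 4 weeks.

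For the cycle 2 PK trough, Section 4.2.3 accepts a sample on Day 1 of cycle 3 only if the subject's "last dose of study treatment was the evening prior". The cytokine draws carry no such condition.

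**The concern.** The contrast is meant to show what about four weeks of PTC299 does to circulating angiogenic factors. If the sample that stands in for Day 28 waits for a late cycle 2, it is taken after one to four weeks without drug, and nothing in Section 11.2 flags it or handles it differently.

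At stake is secondary objective 2.2.2. Section 1.2.5.3 suggests that a fall in circulating tumour-derived VEGF may be mechanism-specific evidence of activity in patients. Off-drug values in an on-treatment contrast would understate such a fall. Because the same value is the reference for the later minimum, they could also suggest an effect that deepens over time when it does not.

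**Working it through.** The documents give no sample size, power or expected effect for these endpoints, so there is no stated figure to reproduce. The check covers dates, drug remaining, and the consequence for the two contrasts.

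**1. Dates.** Cycle 1 lasts 28 days, so an undelayed cycle 2 starts on Day 28 + 1 = 29. With a delay of w weeks it starts on Day 29 + 7w, that is Day 36, 43, 50 or 57. If the calendar label governs instead, the 3-day window in Section 4.2 puts the draw on Day 26 to 32.

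**2. Drug remaining.** Section 1.2.6.1 gives a terminal half-life "in the range of 28 to 56 hours". Fraction remaining = 0.5^(hours off drug / half-life).

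| Start of cycle 2 | Hours off drug | Half-lives (56 h to 28 h) | Drug remaining |
|---|---|---|---|
| On time, trough | 12 | 0.2 to 0.4 | 86% to 74% |
| 1 week late | 168 | 3 to 6 | 12.5% to 1.6% |
| 2 weeks late | 336 | 6 to 12 | 1.6% to 0.02% |
| 4 weeks late | 672 | 12 to 24 | 0.02% or less |

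An on-time pre-dose draw is therefore an ordinary trough.

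**3. Against the target concentration.** Days to fall below target = half-life × log2(C / target) / 24. Inputs are the Day 7 C24h means in Table 2, the target of 0.10 to 0.15 µg/mL, and the extreme mean half-lives in Table 1 (28.3 and 55.8 h).

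- 78 mg BID, C = 0.85 µg/mL: 3.0 to 7.2 days.
- 103 mg TID, C = 2.37 µg/mL: 4.7 to 10.6 days. The upper end is 55.8 × log2(23.7) / 24.
- About 200 mg TID, C = 2 × 2.37 = 4.74 µg/mL (assumes dose proportionality): 5.9 to 12.9 days.

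A delay of 14 days or more is below target in every case. A delay of 7 days is borderline, particularly at the higher exposures.

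**4. First contrast, Day 28 against baseline.** Let Δ be the true mean fall on drug and f the share of subjects sampled after the effect has gone. The observed fall is (1 − f)Δ. The documents do not give f. Over an assumed range, f = 1/12 keeps 92% of the effect, 2/12 keeps 83% and 1/3 keeps 67%.

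As an illustration, take a two-sided 5% paired t-test at n = 12, the Stage 3 minimum at the top dose in Section 11.1. Suppose it has 80% power undiluted, which needs a standardised change d = 0.89. With the mean at (1 − f)d and the SD at √(1 + f(1 − f)d²), power becomes 70%, 60% and 41% for the three values of f.

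**5. Second contrast, Day 28 against the later minimum.** If the later minimum lies δ below the true on-drug Day 28 level, the intended contrast is δ. For a subject whose Day 28 value has returned to baseline it is Δ + δ, so the group mean becomes δ + fΔ. The share lost from the first contrast reappears in the second.

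**The case against.** The best defence is that the schedule already means calendar Day 29. Appendix I footnote 7 gives cytokines the same Day 29 label as the blood counts, chemistries and toxicity evaluation, which are the assessments that show whether cycle 2 can start. A site could well hold the visit on Day 29, draw everything, and then decide on cycle 2. The draw would then fall on Day 26 to 32. This is a fair reading, and it makes the plan ambiguous rather than plainly wrong. It does not settle the matter, because Section 4.2.4 names only Day 1 of the cycle, and the last-dose condition in 4.2.3 shows that Day 1 of a cycle was not assumed to follow directly on dosing.

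Three limits also stand. The objectives are secondary and descriptive, and a Day 15 cytokine sample exists. The compliance log in Appendix XI records doses by date and time of day, so time off drug can largely be recovered. And the half-life describes drug, not effect: the only offset time given is in vitro, for the cell cycle ("with reversion to normal cell cycle progression by ~24 hours after cessation of drug exposure"), and none is given for circulating cytokines.

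A reader might go further in three directions that the documents do not support.

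- **CD4, HIV RNA and KSHV load.** These are not in the Day 28 contrast. Section 11.2 analyses them by repeated-measures ANOVA at the indicated sampling times. Their schedule names the calendar day first ("CD4 count on Day 29 (Day 1 of cycle 2) and every three cycles (12 weeks) thereafter"; "Plasma HIV-1 RNA on Day 29 (Day 1 of cycle 2) and every three cycles (12 weeks) thereafter"), so the label is only ambiguous. Loss of effect on them cannot be inferred from drug half-life.
- **A flattened dose comparison.** It is tempting to suppose that delays cluster at higher doses. Section 1.2.6.2 reports adverse events that did not depend on dose, and Section 5.3.6 reports no drug-related events in 12 cancer patients (6 + 6). Those exposures were lower or shorter than in Stage 3, so they do not exclude such a bias, but nothing shows it.
- **The biopsies.** They are fixed to Days 22 to 28 and do not move with cycle 2. The remaining question there is only whether drug was being withheld at the time.

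**Conclusion.** The concern holds for VEGF, VEGFR and cytokines. Section 11.2 analyses a value that the schedule does not collect, and the literal text of 4.2.4 replaces it with one that may be taken up to 4 weeks off drug. After 2 weeks at most about 1.6% of drug remains; after 1 week 1.6% to 12.5%, which is borderline at higher exposures.

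The size of the bias is open. It affects only subjects whose cycle 2 is delayed, and it equals their share times whatever part of the effect has been lost. The dilution and power figures assume that share and assume complete loss of effect. The drug-remaining figures assume that single-dose half-lives from healthy volunteers apply to KS patients on repeated dosing. The primary objectives and dose-escalation decisions are untouched, but the correction is worth making because it is specific and cheap.

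**What to change.** - **Section 4.2.4 and Appendix I.** Draw the end-of-cycle-1 cytokine sample at the existing Day 28 PK visit, or on calendar Day 29 within the window, whether or not cycle 2 starts on time. State that the calendar day also governs the CD4, HIV RNA and KSHV draws.
- **Section 11.2, definition.** Define the Day 28 value as that sample. For the 17 subjects already enrolled in Stages 1 and 2 (9 + 8), name the Day 29 / cycle 2 Day 1 sample as the fallback.
- **Time since last dose.** Derive it from the dosing diary for every pharmacodynamic blood sample and for the Day 22 to 28 biopsies. A calendar-fixed sample can still be off drug if dosing was interrupted within cycle 1.
- **Section 11.2, analysis.** Keep all values in the main analysis, so that subjects with interrupted dosing are not selected out of small cohorts. Pre-specify a sensitivity analysis restricted to values taken on drug, meaning a last dose on the same day or the evening before. This adapts the PK trough condition, which mentions only the evening before and sets no limit in hours.

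The cost is one tube moved to a visit that already takes place, one derived variable and one extra analysis. Dosing and delay rules are unchanged.
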